2.5.2 Statistical hypothesis, model, and method of analysis

The primary analysis of this study will be descriptive without any formal group comparisons or hypothesis testing. The absolute and relative frequencies of patients achieving a DLQI 0/1 response, i.e. a DLQI score of 0 to 1, at Week 16 will be calculated for the subpopulations as well as for the overall study population. For the proportions, (descriptive) 95% CIs will additionally be reported.

The proportion of DLQI 0/1 response at Week 16, overall and by subpopulation, will be presented graphically.

Details how to derive the DLQI score are given in the [Appendix 5.4.1](#).

2.5.3 Handling of missing values/censoring/discontinuations

The last observation carried forward (LOCF) method will be applied to the continuous variables of DLQI score that are missing after baseline regardless to the reason for missing data (e.g. premature study discontinuation, missed visit, administrative issues). The binary response variable based on DLQI score will be derived from these imputed values, this means that a patient with missing values will be counted as a non-responder unless he already achieved the respective response criterion at the last available measurement. Baseline values will not be carried forward. LOCF will be applied to all post-baseline visits.

LOCF imputation:

1. Assign analysis visit windows as described in [Section 2.1.1](#) per assessment date for unscheduled visits.
2. If no eCRF visit is assigned to an analysis visit as per [Section 2.1.1](#), impute with LOCF

Any missing individual items are treated as missing data. Handling of missing items within the DLQI questionnaire is described in the [Appendix 5.4.1](#).

The percentage of missing items in the DLQI questionnaire and will be presented over visits. In addition the percentage of scores/index values imputed with LOCF will be presented by visit.

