1.1 Background

Psoriasis is an immune-mediated, chronic relapsing inflammatory disease that mainly affects the skin and is characterized by variable clinical features. Plaque (also called plaque-type or chronic plaque) psoriasis is the most frequent clinical presentation. Chronic plaque psoriasis can have a profound impact on several aspects of a patient's life. Psoriasis affects not only the skin itself but has been demonstrated to be closely related to the deterioration of patient's emotional, social, occupational, and physical functioning (Eskin et al 2014). The impact of untreated chronic psoriasis on quality of life (QoL) has been demonstrated to be similar to the effects of cancer or congestive heart failure (Bhutani et al 2013). For these reasons, understanding the patient's perspective on their psoriasis and impact on daily activities and disease treatment is a critical component of clinical research and practice.

Broadly accepted assessment systems to measure the effect of psoriasis treatments on patients through a clinician-reported outcome are the Psoriasis Area and Severity Index (PASI) or the Investigator Global Assessment (IGA) (Feldman et al 2005; Langley et al 2013). The correlation between clinician-reported outcomes and patient-reported outcomes (PROs) has been studied to some extent (Revicki et al 2008); however, a better understanding from the view of the patient on the individual impact on the disease, influencing factors and effect of secukinumab during short and long term treatment is needed. Several PRO measures are available for psoriasis evaluation and are starting to be included as valuable endpoints in clinical trials (Gniadecki et al 2012, Revicki et al 2007, Lebwohl et al 2010, and Viswanathan et al 2014). A combination of general health-related, dermatology-related and psoriasis-related questionnaires provides a comprehensive overview from different patient perspectives.

The EuroQOL 5-Dimension Health Questionnaire[®] (EQ-5D[®]) assesses each subject's overall health status and is a standardized tool for measuring health outcomes. It has been extensively used in several dermatological conditions including psoriasis (Rønneberg Mehren et al 2014). The tool was used during the Phase 3 clinical program for secukinumab.

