5.6.2 Discontinuation of study treatment

If discontinuation occurs for any reason in a treatment period (i.e. Treatment Period 1 or 2), the Investigator/qualified site staff must make every effort to determine the primary reason for the patient's discontinuation from the study. This information will then be recorded by Investigator/qualified site staff in the applicable eCRF section.

The study drug must be discontinued under the following circumstances:

- Withdrawal of informed consent.
- Emergence of the following AEs: AEs that in the judgment of the Investigator/qualified site staff (taking into account the patient's overall status) prevent the patient from continuing participation in the study (for example, sepsis or serious infection).
- Any laboratory abnormalities that in the judgment of the Investigator/qualified site staff (taking into consideration the patient's overall status) prevents the patient from continuing participation in the study.
- Pregnancy (see [Section 6.5.5](#) and [Section 7.3](#)).
- Use of prohibited treatment as per guidance in [Section 5.5.8](#).
- Any other protocol deviation that results in a significant risk to the patient's safety.

Patients discontinued from study drug will NOT be considered discontinued from the study. On the applicable section of the eCRF, the Investigator/qualified site staff must record the date and primary reason for stopping the study drug.

At the time of the study drug discontinuation visit,

- IF it has been at least 4 weeks after the last dose of study drug, THEN the assessments described for the end of Treatment Period 1 (EOT1) visit/Week 16 (for early discontinuation during Treatment Period 1) or the end of the Treatment Period 2 (EOT2) visit/Week 52 (for early discontinuation during Treatment Period 2) should be completed at this visit.

- IF it has not been at least 4 weeks after the last dose of study drug at the time of the study drug discontinuation visit, THEN the patient should be scheduled to return 4 weeks post last dose for their EOT1 visit (Week 16) or EOT2 visit (Week 52) assessments, respectively.

The Investigator/qualified site staff must contact the electronic study system on every study visit including when the patient completes the EOT1 visit (Week 16) or EOT2 Visit (Week 52) assessments to register the patient's completion of the study (Treatment Period 1 or 2, respectively) due to study drug discontinuation.

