2.5.4 Supportive analyses

No sensitivity analysis will be performed.

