2.7.3 Handling of missing values/censoring/discontinuations

The last observation carried forward (LOCF) method will be applied to all secondary variables.

Any missing individual items will not be imputed. Handling of missing items within each questionnaire is described in the [Appendix 5.4](#).

For each questionnaire, where it is allowed to skip questions (DLQI, HAQ-DI, PBI, TSQM [REDACTED]), the percentage of missing items and will be presented over visits. In addition the percentage of scores/index values imputed with LOCF will be presented by visit.

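### At Week 52, carrying the last score forward whatever the reason for stopping counts patients who left treatment while responding as responders, and no planned table shows how many they are.

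*SAP*

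**What the plan says.** **Imputation.** SAP 2.5.3 applies LOCF to the DLQI score whatever the cause of the missing value, with premature discontinuation among its examples. The binary response is then derived from the imputed score: "a patient with missing values will be counted as a non-responder unless he already achieved the respective response criterion at the last available measurement". Baseline is not carried, but otherwise "LOCF will be applied to all post-baseline visits". SAP 2.7.3 says the same "method will be applied to all secondary variables", and SAP 2.7.2 confirms that by-visit summaries use LOCF. The rule therefore governs Week 52 DLQI 0/1, PASI 50/75/90/100 and IGA 0/1. Protocol 9.4.3 gives the same rule for DLQI, PASI and IGA.

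**Last assessment after stopping.** Protocol 5.6.2 has the end-of-treatment assessments done at the discontinuation visit if at least 4 weeks have passed since the last dose. Otherwise, "THEN the patient should be scheduled to return 4 weeks post last dose". That visit is registered as completion of the treatment period. Protocol Section 6, under the visit windows, provides only a 4-week follow-up after premature discontinuation. Yet 5.6.2 also states: "Patients discontinued from study drug will NOT be considered discontinued from the study".

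**Disease course.** Protocol 1.1: "Psoriasis is an immune-mediated, chronic relapsing inflammatory disease".

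**Checks on the rule.** SAP 2.5.4: "No sensitivity analysis will be performed"; Protocol 9.4.4 agrees. The SAP does report the percentage of scores imputed by visit (2.5.3, 2.7.3), discontinuations with reasons by phase and subpopulation (2.3.1), and exposure thresholds up to 52 weeks (2.4.1).

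**The concern.** Four weeks is the maintenance dosing interval, and completers are themselves assessed at Week 52, 4 weeks after their Week 48 dose. For a patient who stops and is seen on schedule, the carried score is therefore effectively an on-treatment value. Using it at Week 52 assumes that response persists, untreated and unobserved, for up to most of a year. Nothing in the documents supports that assumption.

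The Week 52 rate then mixes two kinds of responder: patients still treated and observed, and patients who left while responding. Protocol 3.2 gives the 52-week period the purpose of assessing the long-term impact of prior treatment. If subpopulations A, B and C differ in how often or why patients stop, the mixture differs between them, and so does the apparent contrast. The planned tables show how many patients stopped, why, and how many scores were imputed. They do not show how many imputed scores are responses, so a reader cannot separate the two groups.

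**Working it through.** **1. The plan's own figure.** Protocol 9.7 and SAP Section 3 use a 70% rate and 5-point precision. Reading 5 points as the half-width of the 95% CI: n = 1.96² × 0.70 × 0.30 / 0.05² = 322.7, so 323. The total is 323 / 0.20 = 1615. Both reproduce. They concern Week 16 and do not depend on the imputation rule.

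**2. How long a score is carried.** Take the last visit as 4 weeks after the last dose (Protocol 5.6.2):

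| Last dose (week) | Last seen (week) | Carried to Week 16 (weeks) | Carried to Week 52 (weeks) |
|---|---|---|---|
| 0 | 4 | 12 | 48 |
| 8 | 12 | 4 | 40 |
| 12 | 16 | 0 (observed) | 36 |
| 16 | 20 | 0 (observed) | 32 |
| 24 | 28 | 0 (observed) | 24 |
| 44 | 48 | 0 (observed) | 4 |

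A patient last dosed at Week 12 with DLQI 0/1 at the Week 16 visit is thus a Week 52 responder 52 − 16 = 36 weeks after last being seen and 52 − 12 = 40 weeks after the last dose.

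**3. Size of the effect.** Let d be the share who stop before the visit, r the share of stoppers who are responders when last seen, and p the rate among completers.

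- LOCF rate = (1 − d)p + d·r
- Rate with stoppers as non-responders = (1 − d)p
- Difference = d·r, which does not depend on p

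The documents give neither d nor r. Assumed ranges are 5-20% for d and 20-60% for r. Difference in percentage points:

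| d | r = 20% | r = 40% | r = 60% |
|---|---|---|---|
| 5% | 1 | 2 | 3 |
| 10% | 2 | 4 | 6 |
| 15% | 3 | 6 | 9 |
| 20% | 4 | 8 | 12 |

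**4. One worked case.** Subpopulation C, n = 323, with d = 15%, r = 40% and p = 70% (all assumed for Week 52). Completers responding: 323 × 0.85 × 0.70 ≈ 192. Carried responders: 323 × 0.15 × 0.40 ≈ 19. With the SAP 5.6.1 interval:

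- LOCF: 211/323 = 65.3% (95% CI 59.8-70.5)
- Stoppers as non-responders: 192/323 = 59.4% (53.9-64.8)

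**5. A loose end in the imputation steps.** SAP 2.1.1 re-aligns all visits to windows by day. Step 1 of the LOCF rule in SAP 2.5.3 speaks of assigning windows by date for unscheduled visits, and step 2 imputes only where no eCRF visit falls in the analysis visit. An early end-of-treatment visit is recorded under the Week 52 (EOT2) label. Depending on which text the programmer follows, it could be analysed as observed Week 52 data and drop out of the imputation percentage altogether.

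**The case against.** The rule is disclosed, is the same in protocol and SAP, and sits in a wholly descriptive analysis, so no test is invalidated. Protocol 3.2 frames the question as response while on treatment, and a last on-treatment score fits that framing to some degree. Patients stopped around Week 16 for lack of response would mostly be carried as non-responders, which limits r. Disposition with reasons and exposure by subpopulation already let a reader see differential dropout. All of this stands. It makes the point one of interpretation and reporting, not of error.

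A reader might also infer three stronger things that the documents do not support.

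- *That the Week 16 primary result is materially affected.* A patient last dosed at Week 12 is actually observed at Week 16, and on the 5.6.2 schedule the carry to Week 16 is at most about 12 weeks.
- *That LOCF is biased upward in absolute terms.* It is higher than non-responder counting, but that is a comparison rule and not the truth. The protocol places the efficacy plateau at about Week 16, so an early score carried to Week 16 may even understate response.
- *That the difference exceeds the planned precision.* The 5-point figure was set for Week 16. Seven of the 12 cells in the table above fall below 5 points, as does about 56% of the assumed range under uniform weighting.

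Nor is every stopper seen at 4 weeks. Under Protocol 5.6.3 consent withdrawers have no further assessments (Section 6 offers a visit if the patient agrees). For them the carried value may be older still.

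**Conclusion.** The point holds, mainly for the Week 52 endpoints. As written, the Week 52 DLQI, PASI and IGA response rates include patients who stopped study drug while responding and were not observed afterwards, for up to 36 weeks in the example. The planned output does not let a reader remove them or count them. Relative to non-responder counting, the excess is d·r: 1 to 12 points under assumed stopping of 5-20% and assumed last-visit response of 20-60%. The true size cannot be fixed from the documents. Distortion between subpopulations follows only if d·r differs between them, which is possible but not shown. The sample size is unaffected. This is a worthwhile and inexpensive improvement to a stated rule.

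**What to change.** - **SAP 2.7.2.1 and 2.7.2.2 (and 2.5.2 for completeness):** beside the LOCF rate, overall and by subpopulation, report a rate in which a patient who permanently stopped study drug before the visit is a non-responder. Keep LOCF there only for missed visits of patients still on drug.
- **SAP 2.5.3 and 2.7.3:** beside the percentage imputed, give the number of LOCF-imputed responders by visit and subpopulation.
- **SAP 2.5.4:** replace "No sensitivity analysis will be performed" with a reference to this second rate.
- **SAP 2.5.3:** state that an early EOT2 visit is assigned to an analysis window by its actual date, so that it is not analysed as observed Week 52 data.
- **Protocol 5.6.2 and Section 6:** reconcile the statement that stoppers remain in the study with the provision of only a 4-week follow-up.

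Cost: SAP wording and one more set of proportion tables. The date and reason for stopping are already recorded on the eCRF. A second, less favourable figure will appear beside the LOCF rate; it should be labelled as a conservative bound and not as the true rate.

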2.5.4 Supportive analyses

No sensitivity analysis will be performed.

2.6 Analysis of the key secondary objective

There is no key secondary objective defined for this study.

2.7 Analysis of secondary efficacy objective(s)

2.7.1 Secondary endpoints

- To assess the proportion of patients achieving a DLQI 0/1 response at Week 52 in the 3 subpopulations and in the overall study population.
- To assess the effects of treatment with secukinumab 300 mg with respect to changes in EQ-5D, HAQ-DI, NRS, TSQM and PBI response over time up to Week 16 and Week 52 compared to baseline in the 3 subpopulations and in the overall study population.
- To assess the proportion of patients achieving PASI 50, PASI 75, PASI 90, PASI 100 and IGA mod 2011 0/1 responses at Week 16 and Week 52 in the 3 subpopulations and in the overall study population.
- To assess the proportion of patients with DLQI scores 2-5, 6-10, 11-20, 21-30 at Week 16 and Week 52 compared to baseline in the 3 subpopulations and in the overall study population.
- To assess the overall safety and tolerability of treatment with secukinumab 300 mg in the 3 subpopulations and in the overall study population.

The analyses of the secondary efficacy endpoints will be performed on the FAS, overall and by subpopulation.

The analysis of the secondary endpoint regarding safety will be described in the safety section 2.8.

2.7.2 Statistical hypothesis, model, and method of analysis

As the analysis of the primary endpoint all analyses of the secondary endpoints will be descriptive without any formal group comparisons or hypothesis testing.

Summaries by visit will include the corresponding scheduled visits with missing data imputed using LOCF.

Details how to derive the respective index values and scores are given in [Appendix 5.4](#).

2.7.2.1 DLQI

The absolute and relative frequencies (including 95% CI) of patients achieving a DLQI 0/1 response will be presented by visit, overall and by subpopulation. The proportion of DLQI 0/1 response will be presented graphically over visits.

The absolute and relative frequencies (including 95% CI) of patients achieving a 0 response in a subsection will be analyzed similarly to the DLQI 0/1 response separately for each subsection.

The number and percentages (including 95% CI) of patients in each DLQI score category of 0-1, 2-5, 6-10, 11-20, 21-30 will be presented by visit, overall and by subpopulation. In

addition a shift table using these categories will be presented to compare baseline and Week 16/Week 52 respectively.

The DLQI score and the DLQI subsection scores will be summarized by visit, overall and by subpopulation presenting the baseline value, post-baseline value, change from baseline and percent change from baseline.

2.7.2.2 BSA, PASI and IGA mod 2011

The absolute and relative frequencies (including 95% CI) of patients achieving PASI 50, PASI 75, PASI 90, PASI 100 and IGA mod 2011 0/1 responder will be presented by visit, overall and by subpopulation. The proportion of response over visits will be presented graphically.

The number and percentages (including 95% CI) of patients in each IGA mod 2011 category will be presented by visit, overall and by subpopulation.

BSA score and PASI score will be summarized similarly to the DLQI score. The mean percent change from baseline in PASI score will be displayed graphically over visits by subpopulation.

2.7.2.3 EQ-5D

The number and percentages (including 95% CI) of patients in each The EQ-5D answer and response category will be presented by visit, overall and by subpopulation.

The EQ-5D VAS and crosswalk index value will be similarly analyzed to the PASI score, presenting the absolute change from baseline in the figure.

2.7.2.4 HAQ-DI

The HAQ-DI disability index will be analyzed similarly to the EQ-5D.

2.7.2.5 NRS

The NRS scales (pain, itching and scaling) will be analyzed similarly to the EQ-5D. The absolute and relative frequencies (including 95% CI) of patients achieving a complete relief of symptom will be presented by symptom (pain, itching, scaling), visit, overall and by subpopulation. The proportion of symptom relief over visits will be presented graphically. A complete relief of symptom is defined as a reply of 0 for the respective symptom.

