Other medical history	X															
Prior and concomitant medications	X	X	X	X	X	X	X	X	X	X	X	X	X	X	X	
Physical examination	S	S	S	S	S	S	S	S	S	S	S	S	S	S	S	
Height	X														X	
Weight	X	X							X					X	X	
Vital signs	X	X				X	X	X	X	X	X	X	X	X	X	

[figure not shown]
		Treatment Period 1							Treatment Period 2							
Period	Scr							EOT1					EOT2	Uns ^d	Comments	
Visit	1	2	3	4	5	6	7	8	9 ^{a, b}	10	11	12	13	14 ^c		
Week	-4 to BL	BL	1	2	3	4	8	12	16	20	24	36	48	52		
Recommended visit window (days)		±2	±2	±2	±2	±5	±5	±5	±2	±5	±5	±5	±5	±5		
Waist and hip circumference	X	X							X					X		
Laboratory sampling: safety panel (clinical chemistry, hematology, urine dipstick)	X	X				X		X	X	X	X	X	X	X	X	Samples will be shipped to the central laboratory for analysis. Urine dipstick to be used locally
Fasting labs: glucose, lipid panel, hsCRP, HbA1C		X							X				X	X		
QuantiFERON [®] TB-Gold in-tube test	X														X	
Serum pregnancy test	X														X	Only for females of child-bearing potential.
Urine pregnancy test (local)		X				X		X	X			X		X	X	In the event of a positive urine pregnancy test, study drug must be withheld and a serum pregnancy test performed at the same visit. A urine pregnancy test is not required for a woman who is sterile or who is post-menopausal.

		Treatment Period 1							Treatment Period 2						
Period	Scr							EOT1					EOT2	Uns ^d	Comments
Visit	1	2	3	4	5	6	7	8	9 ^{a, b}	10	11	12	13	14 ^c	
Week	-4 to BL	BL	1	2	3	4	8	12	16	20	24	36	48	52	
Recommended visit window (days)		±2	±2	±2	±2	±5	±5	±5	±2	±5	±5	±5	±5	±5	
Site assessments:															
IGA mod 2011	X	X	X	X	X	X	X	X	X	X	X	X	X	X	X
PASI	X	X	X	X	X	X	X	X	X	X	X	X	X	X	X
BSA	X	X	X	X	X	X	X	X	X	X	X	X	X	X	X
PRO assessments:															
NRS (pain, itching and scaling VAS)		X				X		X	X		X	X	X	X	X
DLQI		X				X		X	X		X	X	X	X	X
EQ-5D [®]		X				X		X	X		X	X	X	X	X
HAQ [®] -DI		X				X		X	X		X	X	X	X	X
TSQM		X				X		X	X		X	X	X	X	X
PBI		X				X		X	X		X	X	X	X	X
AE assessment (including injection site reactions)	X	X	X	X	X	X	X	X	X	X	X	X	X	X	X
Registration, drug supply, or completion	X ^e	X	X	X	X	X	X	X	X	X	X	X	X	X ^f	^e Registration only ^f Completion only

		Treatment Period 1							Treatment Period 2						
Period	Scr							EOT1					EOT2	Uns ^d	Comments
Visit	1	2	3	4	5	6	7	8	9 ^{a, b}	10	11	12	13	14 ^c	
Week	-4 to BL	BL	1	2	3	4	8	12	16	20	24	36	48	52	
Recommended visit window (days)		±2	±2	±2	±2	±5	±5	±5	±2	±5	±5	±5	±5	±5	

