6.6.1.1 Numeric rating scale: patient's assessment of pain, itching and scaling

A self-administered, 11-point NRS (0-10) will be used to evaluate the patient's assessment of their current pain, itching and scaling. Respondents will answer the following questions for the assessment of:

- Pain: Overall, how severe was your psoriasis-related pain over the past 24 hours?
- Itching: Overall, how severe was your psoriasis-related itch over the past 24 hours?
- Scaling: Overall, how severe was your psoriasis-related scaling over the past 24 hours?

[figure not shown]
Patients have to rate their pain, itching, and scaling from 0 to 10 (11-point scale), with the understanding that 0 represents the absence or null end of the pain, itching, or scale intensity (i.e. no pain, itching or scaling) and 10 represents the other extreme of pain, itching, or scaling intensity (i.e. pain, itching or scaling as bad as it could be). The number that the patient selects represents his or her intensity score.

The NRS scale will be completed by the patient as indicated in [Table 6-1](#).

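### NRS 'complete relief' is any reply of 0 at a visit, so patients already at 0 at baseline count as relieved, and no output in the visible SAP gives the rate among patients who had the symptom

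*SAP*

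**What the plan says.** **Definition.** SAP 2.7.2.5 presents frequencies with 95% CIs of patients achieving complete relief, by symptom and visit, overall and by subpopulation. "A complete relief of symptom is defined as a reply of 0 for the respective symptom".

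**Population.** "The analyses of the secondary efficacy endpoints will be performed on the FAS, overall and by subpopulation" (SAP 2.7.1). The FAS in SAP 2.2 needs one dose and one post-baseline efficacy assessment. Percentages use the relevant population or subgroup as denominator (SAP 2.1), and the only subgroups defined in the visible text are A, B and C (SAP 2.2.1).

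**Entry and scale.** Protocol 4.1 sets minima for PASI, IGA and BSA but none for the NRS. Protocol 6.6.1.1 describes an 11-point scale with a 24-hour recall, on which 0 means that the symptom is absent.

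**Other NRS outputs.** Baseline NRS scores are summarised overall and by subpopulation (SAP 2.3). In addition, "The NRS scales (pain, itching and scaling) will be analyzed similarly to the EQ-5D" (SAP 2.7.2.5). The EQ-5D VAS and index follow PASI (2.7.2.3), PASI follows the DLQI score (2.7.2.2), and the DLQI score gets baseline value, post-baseline value, change and percent change by visit (2.7.2.1).

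**Contrast within the SAP.** For the DLQI score categories, "a shift table using these categories will be presented to compare baseline and Week 16/Week 52 respectively" (2.7.2.1). An IGA 0/1 responder must also improve by at least 2 points from baseline (5.4.2). Neither device is stated for NRS relief.

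**The concern.** Relief is a word for change, but the definition describes a state at one visit. The reported rate therefore pools patients who had the symptom at baseline and lost it with patients who reported none at baseline and still report none. A reader will take the figure as the chance that a patient with pain, itch or scaling becomes free of it, and it is not that.

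Protocol 1.2 gives the purpose as learning whether prior treatment affects quality-of-life outcomes, so the rates for A, B and C will be read side by side. If the share already at 0 at baseline differs between them, the relief rates can differ even when symptomatic patients do equally well in all three.

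**Working it through.** **Inputs.** From the documents: the definition, population and entry criteria above, the planned size of subpopulation C (323), and the CI formula in SAP 5.6.1. Not in the documents: any NRS distribution. So b, q, p and r below are assumptions, shown over ranges.

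**1. The plan's own figure.** The only sample-size figure concerns DLQI 0/1. n = 1.96² × 0.70 × 0.30 / 0.05² = 322.7, rounded up to 323, and 323 / 0.20 = 1615. Both reproduce. The plan states no figure for NRS relief; 323 is used only in step 5.

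**2. Distortion.** The planned rate is r = bq + (1 − b)p, so r − p = b(q − p). It is upward when q > p, zero when q = p and downward when q < p. In percentage points, with q = 90%:

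| b | p = 40% | p = 60% | p = 80% |
|---|---|---|---|
| 5% | +2.5 | +1.5 | +0.5 |
| 10% | +5 | +3 | +1 |
| 20% | +10 | +6 | +2 |
| 30% | +15 | +9 | +3 |

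**3. Subpopulations.** Take the same p = 50% and q = 90% in two subpopulations.
- b = 10%: 0.10 × 0.90 + 0.90 × 0.50 = 54%.
- b = 30%: 0.30 × 0.90 + 0.70 × 0.50 = 62%.

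The 8-point gap comes from baseline mix alone.

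**4. What the planned outputs can recover.**
- *Shares at 0 by visit.* "Summaries by visit will include the corresponding scheduled visits with missing data imputed using LOCF" (SAP 2.7.2), and Protocol Table 6-1 schedules the NRS at Baseline. If the EQ-5D category counts are applied to the NRS, b may be tabulated. These are marginal shares, and p = (r − bq)/(1 − b) still needs q. With r = 66% and q between 80% and 100%, p is 64.2–65.3% (b = 5%), 62.2–64.4% (b = 10%) or 57.5–62.5% (b = 20%). With q left free from 0 to 100%, the b = 20% range widens to 57.5–82.5%, but its upper end needs every patient at 0 at baseline to have the symptom at the visit.
- *Percent change.* SAP 2.1.1 divides the change by the baseline value, so it is undefined at baseline 0. That summary can rest only on patients with the symptom, and reaching 0 is a change of −100%. Its n, against the n for absolute change, indicates how many started at 0. A quartile or median at −100% shows that at least about 25%, 50% or 75% of symptomatic patients reached 0, but not the exact proportion or its CI.
- *Cross-tabulation.* None is stated for the NRS in the visible text.

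**5. Precision after restriction.** Subpopulation C, assumed rate about 60%, SAP 5.6.1 score interval with continuity correction:
- n = 323, 194 events: 54.5–65.4%, half-width 5.5 points.
- b = 20%, so n = 0.80 × 323 = 258, 155 events: 53.8–66.0%, half-width 6.1 points.

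**The case against.** The best defence is that the SAP already holds more than the relief table. Baseline NRS is summarised by subpopulation, and percent change automatically drops patients at 0. Both points stand: a reader might infer that the plan leaves no trace of baseline-0 patients, and that would be wrong. Neither output, however, gives the proportion itself.

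Second, the NRS objective is change over time compared with baseline (Protocol 2.2), which is planned, and reply-of-0 is an added display. DLQI 0/1 is likewise a state with no baseline minimum. This stands and keeps the point small. But the DLQI measure is not called relief, and its categories get a shift table.

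Third, a 0 covers the past 24 hours only. A reader might infer that baseline-0 patients never had the symptom. The recall period does not support that, and some may have had intermittent symptoms. The choice of denominator is therefore partly a judgement, which is a reason to show both rates under accurate names.

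Fourth, SAP 2.11 refers to Section 2.13, which is not shown and could contain the missing table. The statement is limited to the visible text for that reason.

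Fifth, every input on size is assumed. That is so, and no figure above is a prediction.

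**Conclusion.** The point holds as a correction to a descriptive secondary output. The label claims relief, the definition counts anyone at 0, and the visible plan does not report the proportion reaching 0 among patients with the symptom at baseline.

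The size is unknown. It is probably small for scaling, because entry requires IGA of at least 3 and Protocol Table 6-3 describes grade 3 with moderate scaling. For pain the documents set no limit: the survey cited in Protocol 3.2 names itching (43%) and scaling (23%) as most bothersome, gives nothing for pain, and is not a prevalence figure.

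A reader might infer that the relief rates are badly inflated or that the subpopulation results are invalid. The documents support neither. The direction depends on whether q exceeds p, no baseline NRS data are given, and SAP 2.7.2 plans no formal group comparison. What can be said is that unequal baseline shares at 0 could by themselves produce unequal rates. The primary endpoint and the sample size are untouched.

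**What to change.** In SAP 2.7.2.5, report complete relief for each symptom among FAS patients with a baseline score above 0 for that symptom, and show that denominator by subpopulation. Exclude patients with a missing baseline (SAP 2.1.1 allows for them) and count them. Keep the LOCF rule of 2.7.3. Label any whole-FAS share at 0 'symptom-free at visit'. Equally good: a table of baseline (0 versus above 0) against Week 16 and Week 52 (0 versus above 0), modelled on the DLQI shift table. If Section 2.13 already contains such a table, a cross-reference and the new label are enough.

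The cost is two or three sentences and one changed or added table, with no new data. The rates may look less favourable, and intervals widen slightly: by 0.6 points of half-width in subpopulation C in the example in step 5 of the working.
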